# 9.3.1 Variables to determine the primary endpoint(s)

The variables for our primary objective are:

- Compliance to therapy
- Persistence of therapy
- Overall Adherence to therapy

They will be derived in the following way:

Adherence to therapy:

In the medical literature there is no commonly agreed upon definition of adherence. The term adherence has largely replaced the term compliance, as it implies a less directive way of treatment, but acknowledges the patient's participation in the treatment plan in the sense of a shared-decision-making. Beyond this difference in definition both terms refer to the same aspect of treatment, specifically to what extend patient treatment behaviors match the treatment plan. Adherence may be measured in various ways. For our study we will ascertain adherence in different ways to account for different aspects of patient treatment behavior:

- Compliance in percentage—this measure allows a general appreciation of the average patient treatment behavior (and spread) in the whole cohort investigated. It will be calculated as follows:
   Compliance (%) = ((expected # of treatment days during observation period missed # of treatment days during observation period)/(expected # of treatment days during observation period))\*100
- 2. Persistence (dichotomous, yes vs. no)—this measure allows a special view on those patients that completely stopped taking their medication vs. those continuing ("persisting") their medication (regardless of the frequency of intake)
- 3. Overall adherence—this measure will combine compliance and persistence to account for and allow comparison with studies basing their analysis on the "medication possession ratio" (MPR). Patients will be defined as being adherent to therapy if they fulfill the following criteria:
  - a. They have been at least 80% compliant, i.e. injected  $\geq$ 80% of the expected Betaferon® dosages and
  - b. They have not dropped out of the study prior to the time of evaluation (i.e. they did not stop Betaferon® treatment for any reason including switching to another medication prior to the time of evaluation).

Based on this definition adherence will be a dichotomous variable, which can be either "yes" or "no".

4. Number of dosages missed - to further characterize and quantify non-compliance we will also calculate the number of dosages missed

For this study "compliance" in percentage will be our primary outcome variable while persistence and adherence will be considered as co-primary outcome variables.

We will evaluate each of these measures at each of the follow-up visits as well as change from previous follow-up visit starting at follow-up visit 2.

Ascertainment of injection data:

Given the electronic features of the BETACONNECTTM auto-injector, which automatically records injections, we will be able to obtain an unbiased number of injections from patients using this device.

# 9.3.2 Variables to determine the secondary endpoint(s)

These outcome variables for secondary objectives will be collected at each visit:

Satisfaction with the BETACONNECTTM

Satisfaction will be evaluated with the following question on the *patient questionnaire*:

Overall how would you rate your satisfaction with the BETACONNECTTM autoinjector device on a scale from 0 to 10, where "0" means "not satisfied at all" and "10" means "entirely satisfied"? Please mark one of the boxes below.

0	1	2	3	4	5	6	7	8	9	10	
---	---	---	---	---	---	---	---	---	---	----	--

# Injection site pain

Injection site pain will be evaluated with the following question on the *patient questionnaire*:

Overall, when using the BETACONNECTTM auto-injector, how would you rate your intensity of injection site related pain on a scale from 0 to 10, where "0" means "no pain at all" and "10" means the "worst possible pain"? Please mark one of the boxes below.

0	1	2	3	4	5	6	7	8	9	10

Usage of analgesics prior to Betaferon® injection & Flu-like symptoms

Patients will be asked the following questions on the *patient questionnaire*:

- ➤ When using Betaferon® are you using any analgesics prior to injection?
  - a. No
  - b. Yes
- When using Betaferon®, do you experience flu-like symptoms like fever, myalgia, chills, or headaches?
  - a. No

b. Yes

#### Depression

Center for Epidemiologic Studies Depression Scale (CES-D)/ Allgemeine Depressionsskala (ADS-L)

The CES-D is a self-administered questionnaire to measure symptoms of depression experienced during the past week. It includes 20 items comprising six scales reflecting major dimensions of depression: depressed mood, feelings of guilt and worthlessness, feelings of helplessness and hopelessness, psychomotor retardation, loss of appetite, and sleep disturbance.

For this study we will use the ADS-L, which is the validated German translation of the CES-D.

#### • Health related quality of life

#### Short Form-36

The SF-36 is a multi-purpose, short-form health survey with 36 questions designed for use in clinical practice and research, health policy evaluations, and general population surveys. The SF-36 includes one multi- item scale that assesses eight health concepts: 1) limitations in physical activities because of health problems; 2) limitations in social activities because of physical or emotional problems; 3) limitations in usual role activities because of physical health problems; 4) bodily pain; 5) general mental health (psychological distress and well-being); 6) limitations in usual role activities because of fatigue); and 8) general health perceptions. The survey was constructed for self-administration by persons 14 years of age and older, and for administration by a trained interviewer in person or by telephone. Each scale is directly transformed into a 0-100 scale.

# Coping mechanisms\*

# The Coping with MS Scale (CMSS)

The CMSS is a multidimensional coping inventory to assess different ways people with MS respond to illness-related stressors. It consists of 29 items covering seven categories (problem solving, physical assistance, emotional release, avoidance, personal health control, acceptance, energy conservation). Each item can be rated on a seven-point scale (1=not stressful at all to 7=extremely stressful).

#### Self-management mechanisms

Multiple Sclerosis Self-Management Scale-Revised (MSSM-R)

The MSSM-R is a brief and multidimensional scale for research and clinical applications. It was created as an instrument that addresses both the multidimensional nature of self-management in general and those aspects of self-management that may be specific to the experience of persons with MS. It consists of 24 items, each of which can be scored on a 5-point Likert scale (1= I completely disagree to 5=I completely agree). Factor analysis has identified the following five subscales: (1) Healthcare provider relationship and communication; (2) treatment adherence/barriers; (3) Social/family support; (4) MS knowledge and information; and (5) Health maintenance behavior. The composite scale has been found to be correlated with quality of life, self-efficacy, and functional impact scales.

#### Social support\*

#### Inventory of Social Support in Dyads (Inventar zur sozialen Unterstützung in Dyaden; ISU-DYA)

In order to examine supportive interactions within stressful situations it is necessary to consider both providers' and recipients' reports (the "dyad"). The ISU-DYA was developed to retrospectively assess support as well as mobilization behavior in a specific stressful episode from both perspectives of the dyad. Factor analysis has identified five mobilization scales (1. requesting feedback and advice; 2. demanding help; 3. search for physical contact; 4. emotional expression; 5. ostentatious withdrawal) and three support scales (1. emotional, 2. informational, 3. instrumental support).

#### Fatigue

# Würzburger Fatigue Inventory for MS (Würzburger Erschöpfungs-Inventar bei Multipler Sklerose; WEIMuS)

The WEIMuS is a two-dimensional, easy to use self-administered questionnaire in order to appropriately assess MS-associated fatigue. The questionnaire consists of two scales covering both "physical fatigue" (8 items) and "cognitive fatigue" (9 items). Each item can be scored on a scale from 0 to 4.

Cognition

#### The Symbol Digit Modalities Test (SDMT)

The SDMT is used to investigate cognitive functioning over time and in response to treatment with high sensitivity. It is brief and easy to administer, screening for possible motor, visual, learning, or other cerebral dysfunction. The SDMT involves a simple substitution task. Using a reference key, the examinee has 90 seconds to pair specific numbers with given geometric figures. Because examinees can give either written or spoken responses, the test is well suited for use with

individuals who have motor disabilities or speech disorders. Because it involves only geometric figures and numbers, the SDMT is relatively culture free as well and can be administered to individuals who do not speak English.

- number of relapses at 12 and 24 months
- EDSS (Expanded Disability Status Scale)
- utilities of treatment (only at baseline and final visit)
   *Derived from the EQ5-D questionnaire*

The EQ-5D is a health questionnaire providing a one dimensional quality of life assessment. The score ranges from 5 (very good) to 15 (extremely low). It was developed in 1987 by an international interdisciplinary group consisting of physicians, psychologists, philosophers, economists, nurses, and sociologists. The questionnaire evaluates five dimensions of health: mobility, ability to care for oneself, activities of daily life, pain, and anxiety.

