#### 8.2 Secondary objective(s)

Secondary objectives are to evaluate at each visit:

- Satisfaction with the BETACONNECTTM autoinjector,
- Injection site pain,
- Flu-like symptoms following Betaferon® application,
- Analgesic use prior to Betaferon® application,
- Intake of vitamin D, other vitamins, and nutrients,
- If adherence to Betaferon® treatment is associated with:
  - depression,
  - health related quality of life,
  - coping mechanisms\*,
  - self-management mechanisms,
  - social support\*,

- fatigue, and
- cognition.
- If adherence to Betaferon® treatment at 12 (24) months is associated with number of relapses at 12 (24) months.
- If adherence to Betaferon® treatment at 12 (24) months is associated with EDSS change at 12 (24) months.
- If adherence to Betaferon® treatment is associated with utilities of treatment (only baseline and final visit).
- With respect to the subgroup of patients participating in the PTMS program (participants from PTMS centers vs. participants from non-PTMS centers):
  - At each visit, if the PTMS program is associated with:
    - treatment adherence,
    - depression,
    - quality of life,
    - self-management mechanisms,
    - fatigue,
    - cognition.
- In the subgroup of patients participating in the PTMS program:
  - At each visit evaluation of:
    - social support,
    - coping behavior.

\*only for patients participating in the PTMS program.

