# 9.1.2 Secondary endpoint(s)

The secondary endpoints are:

- Satisfaction with the BETACONNECTTM autoinjector
- Injection site pain
- Flu-like symptoms

- Analgesic use prior to Betaferon® application
- Intake of vitamin D, other vitamins, and nutrients
- Depression
- health related quality of life
- coping mechanisms\*
- self-management mechanisms
- social support\*
- fatigue
- cognition
- number of relapses at 12 and 24 months
- EDSS change at 12 and 24 months
- utilities of treatment

\*to be evaluated only in the subgroup of patients participating in the PTMS program.

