# 9.3 Variables

The investigator collects historic data (demographic and clinical characteristics) from medical records if available, or else by interviewing the patient. Likewise, the investigator collects treatment related data during initial visit and follow-up visits. The investigator documents the study-relevant data for each patient in the electronic case report form (eCRF). All variables as indicated in **Table 1** are routinely collected during regular office visits. The CRF is available upon request (see Table 2: List of stand-alone documents, Annex 1).

Variables	Initial visit	Follow-up visit 1	Follow-up visit 2	Follow-up visit 3	Final visit
Demography	Х				
Employment status	Х	X	Х	X	Х
Education	Х				
Smoking	Х	X	Х	X	Х
Vitamin D intake	Х	Х	Х	X	Х
Other vitamin or nutrient intake	Х	Х	Х	X	Х
Medical history	Х				
Specific MS history	Х	X	Х	X	Х
Concomitant medication	Х	X	Х	X	Х
Concomitant diseases	Х	Х	Х	X	Х
Disease course		X	Х	X	Х
Expanded Disability Status Scale	Х	X	Х	X	X
Local skin reactions	Х	X	Х	Х	Х

Table 1: Tabulated overview on variables collected during the study

			-		
Expected/true treatment days	Х	X	X	Х	Х
Symbol Digit Modalities Test (SDMT)	Х		X		X
Participation in the BETAPLUS ® nurse support program	Х	X	X	Х	X
Participation in the PTMS program	Х	X	X	Х	X
Satisfaction with current way of Betaferon ® injection	Х	X	Х	Х	X
Injection site pain with current way of Betaferon ® injection	Х	X	X	Х	X
Flu-like symptoms following application of Betaferon ®	Х	X	Х	Х	X
Prophylactic analgesic use prior to Betaferon ® injection with current way of injection	Х	X	X	Х	X
Using electronic features of BETACONNECT TM	Х	X	X	Х	X
CES-D questionnaire (depression)	Х	Х	X	Х	Х
SF-36 questionnaire (HrQoL)	Х	X	X	Х	X
EQ-5D (utilities)	Х				Х
WEIMuS questionnaire (fatigue)	Х	Х	X	Х	Х
MSSM-R questionnaire (self- management)	Х	X	X	Х	X
CMSS questionnaire (coping)*	Х	X	X	Х	X
ISU-DYA Inventory (social support)*	Х	X	X	Х	X
Adverse Events		X	X	Х	Х
Medical Device related events and PTCs (including use errors)		X	X	Х	X
Reason for end of observation					Х

\*only for patients in centers, where the PTMS program is offered

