## 9.7 Data analysis

#### 9.7.1 Statistical considerations

Statistical analyses will be of explorative and descriptive nature. P-values <0.05 will be considered as statistically significant unless stated otherwise.

All variables will be analyzed descriptively with appropriate statistical methods: categorical variables by frequency tables (absolute and relative frequencies) and continuous variables by sample statistics (i.e. mean, standard deviation, minimum, median, quartiles and maximum). Continuous variables will be described by absolute value and as change from baseline per analysis time point, if applicable.

All analyses will be performed for the total study population (overall analysis) or when defined otherwise within a valid subpopulation. Patients receiving at least one dose of Betaferon® will be included in the analysis. Whenever reasonable, data will be stratified by subgroups (e.g. age, gender, baseline characteristics).

There will be no further documentation of patients fulfilling the following criteria (end of observation visit will be documented): 1. patients terminating Betaferon® treatment including those stopping treatment overall or switching to other treatments; 2. patients lost to follow-up; and 3. patients choosing to terminate study participation for any reason. During the final visit (in case of premature termination) the investigator should try to identify the date, when Betaferon® treatment was discontinued. If this date cannot be identified or approximated, e.g. if a patient is lost to follow-up, the date of the last documented visit should be chosen. Further, the investigator should make every effort to identify the reason, why a patient decides to terminate the study. Reasons for study termination will be displayed using descriptive statistics.

All therapies documented will be coded using the World Health Organization – Drug Dictionary (WHO-DD). Medical history, any diseases and AEs will be coded using the latest Medical Dictionary for Regulatory Activities (MedDRA) version.

All statistical details including calculated variables and proposed format and content of tables will be detailed in the Statistical Analysis Plan (SAP). The SAP will be finalized before study database lock. The SAP is available upon request (see BF1502\_SAP\_final\_yyyymmdd Table 2: List of stand-alone documents, Annex 1).

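### The utilities endpoint is described only by a 5-to-15 EQ-5D score, which is not a utility and runs in the opposite direction

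*Protocol*

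**What the plan says.** Protocol section 8.2 asks whether adherence is associated with "utilities of treatment (only baseline and final visit"). Section 9.1.2 lists "utilities of treatment" among the secondary endpoints, and the visit table in section 9.3 labels the instrument "EQ-5D (utilities").

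The variable is described at the end of section 9.3.2, in the text that follows the Symbol Digit Modalities Test. Under the utilities bullet it says "Derived from the EQ5-D questionnaire". It then introduces the instrument: "The EQ-5D is a health questionnaire providing a one dimensional quality of life assessment". The scoring follows: "The score ranges from 5 (very good) to 15 (extremely low"). The dimensions come last: "The questionnaire evaluates five dimensions of health: mobility, ability to care for oneself, activities of daily life, pain, and anxiety".

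The protocol mentions no preference weights, value set or index score. On derived variables in general, section 9.7.1 says: "All statistical details including calculated variables and proposed format and content of tables will be detailed in the Statistical Analysis Plan (SAP").

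**The concern.** A utility is a preference-weighted value for a health state, with better health scoring higher. The score printed under the utilities bullet shows neither property. Its best value is its lowest, and its range looks like a count of response levels.

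Two things are at stake. First, an analyst who follows the only scoring in the protocol would report a level count under the name of a utility. Second, the direction is reversed. If better adherence goes with better health, its coefficient is positive on a utility and negative on the 5-to-15 score. An increase from baseline to the final visit would likewise mean improvement on one scale and deterioration on the other.

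**Working it through.** **Inputs, all from the protocol**
- Number of dimensions: 5 (section 9.3.2).
- Stated range: 5 (best) to 15 (worst) (section 9.3.2).
- Levels per dimension: not stated, so tried as L = 2, 3, 4 and 5.

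**Step 1: reproduce the stated range.** Code each dimension 1 to L and add the five codes without weights. The minimum is 5 × 1 = 5 and the maximum is 5 × L.

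| L | Range | Profiles (L^5) | Distinct sums (5L − 5 + 1) |
|---|---|---|---|
| 2 | 5–10 | 32 | 6 |
| 3 | 5–15 | 243 | 11 |
| 4 | 5–20 | 1,024 | 16 |
| 5 | 5–25 | 3,125 | 21 |

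Of the level counts tried, only L = 3 gives the protocol's 5 to 15. The stated figure is therefore reproduced as an unweighted sum of five three-level items.

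**Step 2: what the sum discards.** The 243 profiles fall on 11 values. A sum of 7 arises from one dimension at level 3 with the rest at level 1 (5 profiles), or from two dimensions at level 2 with the rest at level 1 (C(5,2) = 10 profiles). That makes 5 + 10 = 15 profiles with the same score. A sum of 10 covers 51 profiles. Every dimension and every level step counts equally, so the score leaves no place for preference weights.

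**Step 3: direction.** Moving any one dimension to a worse level raises the sum, whereas a utility should not rise. An association with adherence is therefore expected to have opposite signs on the two scales. Rescaling as (15 − S)/10 turns 5 into 1, 7 into 0.8 and 15 into 0. This repairs the direction only: the 15 profiles that scored 7 all score 0.8, and the weights are still absent.

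**Step 4: could the score belong to another endpoint?** The visit table in section 9.3 assigns health-related quality of life to the SF-36 and utilities to the EQ-5D. The EQ-5D serves no other listed endpoint, so the 5-to-15 score cannot be read as describing a different outcome.

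A utility itself cannot be computed here, because the protocol gives no value set.

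**The case against.** The best defence is that the 5-to-15 sentence is background on the instrument and not a scoring rule. It sits beside the year of development and the make-up of the developing group, and other questionnaires in section 9.3.2 get similar sketches. The statement that the endpoint is derived from the questionnaire is compatible with applying a value set. Section 9.7.1 leaves calculated variables to the SAP, which is not at hand. Sections 9.7.4 and 9.7.5 name no analysis of a 5-to-15 score.

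Much of this stands. The absence of a value set from the protocol is not a fault in itself, and the protocol does not commit the analysts to the sum. It also labels both ends of the range, so a careful reader can see the direction.

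What does not fall away is that the only score described for an endpoint called utilities is not a utility. An SAP that followed the description would carry the mismatch forward, and one that used a weighted index would depart from the only scoring the protocol gives. Either way the two need to be reconciled.

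A reader might infer more: that the study will certainly analyse no utilities, that a QALY result is compromised, or that a particular national value set is required. The documents support none of these. The derivation is left open, no QALY or cost-utility analysis is planned, and nothing in the protocol points to a specific value set.

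**Conclusion.** The point holds as a misdescription of one endpoint. The protocol promises utilities and describes a score without preference weights that rises as health worsens. If that score were analysed as described, the adherence–utilities objective would not be answered on a utility scale, and the sign of the association would be opposite to that of a utility.

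This rests on one inference: that 5 to 15 is an unweighted sum of five three-level items. The protocol says neither that items are summed nor how many levels they have. The reversed direction does not depend on the inference, since the protocol states which end is good.

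The reach is small. It concerns one of 15 listed secondary endpoints, measured at two visits, in a study whose analyses section 9.7.1 calls exploratory and descriptive. The primary and co-primary endpoints and the sample size are unaffected.

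**What to change.** Choose one of two wordings.

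- **Keep utilities.** Define the endpoint as the preference-weighted EQ-5D index, higher meaning better, and name the questionnaire version and the value set in the protocol or the SAP. Remove the 5-to-15 range from section 9.3.2, or mark it as a descriptive summary that is not the utility.
- **Keep the score.** Rename the endpoint an EQ-5D sum score, higher meaning worse, state how it is formed, and drop the term utilities wherever it appears: the study information table, the abstract, sections 8.2 and 9.1.2, the visit table in 9.3, and section 9.3.2.

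The first serves the stated objective. Either costs a few lines of text and, for the index, a scoring routine. The EQ-5D is already scheduled at the initial and final visits, with completed forms returned, so no new data are needed.

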#### 9.3.3 Demography

For demographic / socio-demographic assessment, the following data will be recorded:

- Date of birth (at least year)
- Sex (female, male)
- Race / ethnicity (Caucasian, asian, black, other)
- Height (cm)
- Weight (kg)
- Marital status (married/partnership, single)
- Employment status (employed, retired, keeping house, student, seeking work, self-employed, other, not reported)
- Education level (elementary education, secondary education, college or university education, not reported)
- Smoking (current, past, never)
- Intake of vitamin D supplements (yes vs. no; if yes which dosage?)
- Intake of other nutrients or vitamins (yes vs. no)

